1.1 Background

In partnership with clinical experts, Procyron, Inc. (Procyron) has developed a partial Mechanical Circulatory Support (MCS) system to treat patients with Acute Decompensated Heart Failure (ADHF).

Heart failure (HF) is common, affecting more than 6 million adults and resulting in over 1 million annual hospitalizations in the United States alone.¹ HF is a chronic, progressive condition, marked by episodes of acute decompensation typically requiring hospitalization for stabilization and improvement in symptoms. Unfortunately, outcomes after a hospitalization for decompensated heart failure are poor. The 1-year mortality rate after a heart failure hospitalization has remained high at 20-30%,² and there is additive risk with each subsequent hospitalization.^{3,4}

For patients with chronic, stable HF there are multiple pharmacologic and device-based treatment options.^{1,5-7} However, for patients with ADHF, many medical therapies have been tested in this patient population without success⁸⁻¹⁰ and, as a result, acute HF care remains largely homogenous and unchanged over the past 40 years.^{11,12} The majority of acute HF patients are treated with intravenous loop diuretics with consideration of vasodilator therapies.¹³ High-risk patients with decompensated HF failing conventional therapies are rarely (<2%^{14,15}) considered for temporary or permanent MCS due to a lack of evidence in this population, risk, and cost.¹¹ Positive inotropes are similarly uncommon, used in only 6-12% of these patients due to evidence showing worsened outcomes and higher mortality.^{16,17} Despite optimal medical therapy, 33% of ADHF patients are discharged with persistent congestion.¹⁸

Some degree of renal dysfunction occurs in 91% of ADHF admissions, with 64% of patients having at least moderate (Stage III) dysfunction.¹⁶ These patients represent a particularly high-risk population with poor outcomes. Data from the ADHERE registry of over 110,000 ADHF admissions showed that in-hospital mortality increased from 1.9% for patients with normal renal function to 7.6% in patients with severe dysfunction.¹⁶ In these patients, outcomes are poor due to persistent congestion (90% have persistent congestion after 3 days of pharmacologic therapy¹⁹), increased dose of diuretics,²⁰ and decreased diuretic efficiency.²¹

Cardiorenal syndrome (CRS) encompasses a spectrum of disorders involving both the heart and kidneys in which acute or chronic dysfunction in one organ may induce acute or chronic dysfunction in the other organ. The pathophysiology underlying CRS is poorly understood and probably multifactorial, reflecting underlying renal dysfunction from heart failure and other conditions, side effects of acute therapies including diuretics, impaired renal perfusion, and renal congestion.²² The degree of renal dysfunction has not been shown to be directly correlated with the degree of left ventricular systolic dysfunction (reduced ejection fraction), and may also be associated with diastolic dysfunction (preserved ejection fraction). Therefore, the renal dysfunction represents a separate and distinct risk factor for patients with heart failure resulting in reduced (HFrEF) or preserved (HFpEF) ejection fraction patients.¹⁶ Therapies that reduce congestion without causing worsening renal function (WRF) have been elusive, as evidenced from the data in recent trials using low-dose dopamine and nesiritide.²³ There is an urgent need to develop new treatment strategies that will favorably alter the course of this common condition. In fact, the most recent version of the ACC/AHA Heart Failure Guidelines identified the lack of recognition and

treatment of CRS as a key gap in heart failure knowledge and evidence.¹¹ A clinical need exists for a minimally invasive device for treating HF that provides both cardiac and renal support to improve outcomes in the ADHF patient population.

Existing percutaneous impeller pumps and pulsatile balloon pumps placed in the heart have not been shown to be effective in this patient population. Additionally, existing continuous flow percutaneous impeller pumps are placed across the aortic valve, lack sufficient anchoring for patient mobility and safety, and have a high incidence of hemolysis.²⁴

The investigational device, the Aortix System, includes an electrically driven micro-pump with an integrated nitinol stabilization system. The 18F device is deployed trans-femorally to the descending thoracic aorta where the struts, once deployed, expand to stabilize the Aortix Pump to the vessel wall. Once implanted and activated, the Aortix Pump is designed to reduce load on the heart and increase end-organ perfusion, in particular improving flow to the kidneys. When therapy is complete, the device is retrieved via catheter in a similar procedure.

The Aortix System has undergone extensive pre-clinical verification and validation studies to confirm device performance and safety requirements following internationally recognized standards and guidance. The Aortix System has also been tested *in vivo* using large-animal (porcine and ovine) models, successfully demonstrating deployment, retrieval, and acute efficacy. Initial safety and efficacy data were obtained in a porcine model and demonstrated proof of concept (n=9).²⁵ In an ovine model of chronic HF (n=4), the Aortix Pump decreased the energy consumption of the heart by 39%, shifting it to a more efficient operating point. Cardiac output (+14%) and ejection fraction (+28% [relative]) were significantly increased, as were key measures of renal function, eGFR (+23%) and urine output (+100%). These *in vivo* data supported the use of the Aortix System in a first-in-human (n=6) study for acute use during high risk percutaneous coronary intervention (HR-PCI) which demonstrated procedural and device feasibility and safety followed for 14 days.

1.2 Clinical Experience

Procyron completed a first-in-human (FIH) study (n=6) with the Aortix System in the setting of high-risk percutaneous coronary intervention (HR-PCI) procedures.²⁶ The mean number of lesions treated during the procedure was 1.5 (range 1-4).

The Aortix Pump supported the patients during the HR-PCI procedure and was removed at the end of the procedure. The Aortix Pump operated for an average of 70 min (range 47-95) and was deployed in less than 10 minutes in all cases with no device failures. The Aortix Pump operated continuously at an average of 3.5 L/min of estimated pump flow. Angiographic success was achieved in all patients and no episodes of hemodynamic compromise or hemolysis occurred on Aortix Pump support.

Safety, procedural, and efficacy outcomes were assessed. No adverse events or safety issues occurred, and the study generated clinical data suggesting that the Aortix Pump improved both hemodynamics and kidney function.

During therapy, urine output increased an average of 10-fold (n=4 with available data) and serum creatinine decreased an average of 0.12 mg/dL at discharge (n=6) despite contrast load from the HR-PCI procedure.^v Hemodynamics including heart rate and proximal and distal aortic pressures were maintained during and after the HR-PCI procedure.

[figure not shown]
In summary, the Aortix Pump was acutely deployed and retrieved in a simple percutaneous procedure in the setting of HR-PCI (n=6) with 100% angiographic success and no clinical adverse events, adverse device effects, device deficiencies or incidents of hemodynamic compromise were observed. Acute signals from the HR-PCI patient population point to a potential for hemodynamic improvement and a reno-protective effect that could benefit ADHF patients.

2. Device Description

Brief descriptions of the following components of the Procyrion Aortix System are provided below: the Aortix Delivery System, the Aortix Pump, the Aortix Control System, and the Aortix Retrieval System. The Aortix System is investigational. Refer to the Aortix System Instructions for Use (PPL004) for detailed product specifications and instructions for use.

The Aortix Delivery System, Introducer Set and Aortix Pump

The Aortix Delivery System (ADS) is comprised of the Aortix Pump and the Aortix Delivery Tool. The Introducer Set (IS) is comprised of a sheath and a dilator. As described in the Instructions for Use, the Aortix Pump is introduced through the 18F ID/21F OD sheath. The Aortix Delivery Tool allows the Aortix Pump to be connected to and controlled by the Aortix Control System before the Aortix Pump is released from the Aortix Delivery Tool.

[figure not shown]

^v Note the current study protocol for the use of Aortix in ADHF patients with CRS does not require the use of contrast.

Aortix Pump

The Aortix Pump is packaged in the Aortix Delivery System. The Aortix pump is an impeller pump that is approximately 6.5cm long, 6mm (18 F) in diameter (pump body) and implanted in the descending aorta superior to the renal arteries via a femoral approach. Expandable struts maintain the position of the device in the descending aorta while the Aortix Pump provides partial circulatory support at a nominal flow of 3.5 liters per minute. The Aortix Pump has an integral Power Lead (6F in diameter) that exits the arteriotomy and connects to the Aortix Control System. The 6F Power Lead is the only part of the system that exits the arteriotomy; a sheath is not left in for the duration of therapy.

Aortix has no gradient to pump against and uses fluid entrainment to augment pressure and flow in the aorta. In this approach, only a portion of the native blood flow enters the Aortix device. This portion is accelerated by the pump and exits in high velocity jets that entrain, or transfer momentum to, the flow that bypasses the pump. Entrainment allows Aortix to pump effectively while maintaining pulsatile flow. Aortix pumps blood from the aortic root into the abdominal aorta. This decreases aortic root pressure which allows higher cardiac output with less energy required. Downstream of the pump, aortic pressure is higher, driving increases in renal perfusion (flow and pressure).

[figure not shown]
Aortix Control System

The Aortix Control System (ACS) consists of the Aortix Cradle and Aortix Controller. The Aortix Controller is connected to the Power Lead Connector of the Aortix Pump, provides up to approximately 1 hour of battery support when not mounted within the Aortix Cradle, and includes alert indicators. The Aortix Cradle is used to set the Aortix Pump speed, is IV pole mountable, and provides power to the Aortix Controller. The Aortix Cradle displays Aortix Pump operating information and alerts.

The Aortix Retrieval System

The Aortix Retrieval System (ARS) includes (amongst other components) an 18F ID/21F OD Retrieval Sheath and Dilator. The ARS is used to retrieve the Aortix Pump in a second, separate procedure following completion of therapy.

2.1 Indication for Use

Aortix is a circulatory support device for chronic heart failure patients on medical management who have been hospitalized for acute decompensated heart failure (ADHF) with worsening renal function (WRF). Aortix may aid in the treatment of ADHF by providing cardiac and renal circulatory support to decrease congestion and improve renal function resulting in increased urine output and reduced fluid overload.

Currently, the Aortix System is for Clinical Investigational use only, in accordance with this *Clinical Investigation Plan* and subject to required approvals.

2.2 Packaging/Labeling

The Aortix Delivery System and pre-loaded Aortix Pump are packaged together within a sterile barrier and placed in a shelf carton. Product labels are affixed to the pouch and the shelf carton and the electronic *Instructions for Use* (eIFU) card are placed within the shelf carton. The Aortix Introducer Set is packaged separately with an introducer sheath and a dilator. The Aortix Retrieval System components are packaged and labeled in the same way. The Aortix Control System components are packaged together in a foam inset and placed within a shelf carton. Product labels are affixed to the components and the shelf carton and the *Instructions for Use* are placed within the shelf carton.

All product labels include the statement: “Caution: Investigational Device. Limited by Federal (or United States) law to investigational use. Exclusively for clinical investigations.” to comply with United States and international requirements. This device has not been approved for use in any country.

2.3 Sterilization

The Aortix Delivery System (including the Aortix Pump), Introducer Set and the Aortix Retrieval System are provided sterile. The Aortix Delivery System, Introducer Set and Aortix Retrieval System are single-use only and are not to be re-used and are not to be re-sterilized.

The Aortix Control System is packaged in non-sterile packaging. The Aortix Control System components (Cradle and Controller) may be re-used after appropriate cleaning. Refer to the Aortix System Instructions for Use (PPL004) for additional details.

2.4 Shipping/Storage

Good Clinical Practice guidelines require accounting for the disposition of all investigational devices received by each clinical site. Information on device disposition consists of the date received, date used, and the patient in whom the device was used. The Investigator is responsible for accounting for all used and unused devices.

The Aortix System will be hand carried or shipped to the sites at intervals dependent on the rate of patient enrollment. The site will use device accountability forms to document the inventory and study device disposition.

All Aortix System devices for this study must be stored at room temperature in an area free of environmental extremes and with limited, controlled access. Procyrion will inspect the storage area and will ensure study device accountability prior to device use.

Unused product should be returned to the sponsor following final patient enrollment. Expired product can be returned to the sponsor at any time. See Section 4.6 for instructions on returning used product.

3. Study Design

3.1 Study Purpose

The study is a prospective, multi-center, non-randomized feasibility study to evaluate the safety and performance of the Aortix System in patients hospitalized with acute decompensated heart failure (ADHF) irrespective of ejection fraction and worsening renal function refractory to medical management with persistent congestion.

3.2 Study Objectives

To evaluate the Aortix System, specifically to assess:

- Safety:
 - Observe the nature, severity, and frequency of adverse events associated with the delivery, use, and retrieval of the Aortix Pump.
- Performance:
 - Successfully deliver the Aortix Pump to the descending thoracic aorta using the Aortix Delivery System;
 - Aortix Pump shall function as programmed for the duration of therapy;
 - Manage the Aortix Pump Power Lead and access site over the course of therapy without significant complications;
 - Successfully retrieve and remove the Aortix Pump using the Aortix Retrieval System.
- Effectiveness:
 - Evaluate hemodynamic decongestion (CVP, PCWP) during Aortix therapy;
 - Evaluate the effect of the Aortix therapy on kidney function;
 - Evaluate the impact of the Aortix Pump on clinical biomarkers of congestion.

3.3 Study Endpoints

3.3.1 Primary Safety Endpoints

- 1 Rate of Occurrence of Serious Adverse Events (rate will be calculated and reported) [timeframe: enrollment to 30 day visit]
- 2 Rate of Occurrence of Serious Procedure Related Adverse Events (rate will be calculated and reported) [timeframe: procedure to 30 day visit]

3.3.2 Device Performance

1. Deployment (implant) and retrieval procedures success rates (rates will be calculated and reported)

2. Rate of occurrence of ADS, ARS and pump device-related adverse events (includes device malfunctions) (rate will be calculated and reported) [timeframe: implant attempt/implant to 30 day visit]

3.3.3 Primary Effectiveness Endpoints

1. Clinically significant decongestion as measured by the PA catheter. Decrease in CVP or PCWP of $\geq 20\%$. [timeframe: pre-implant vs when congestion target is met or therapy deemed ineffective].
2. Change in Urine Output Assessed as the hourly rate of urine output before pump implanted vs hourly rate of urine output over the Aortix therapy period (until congestion target met or therapy deemed ineffective)
3. Decrease in BNP or NT-pro-BNP by 20% (pre-implant vs when congestion target is met or therapy deemed ineffective)

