4.5 Aortix Post-Deployment Monitoring and Management

The Aortix Pump has been tested to operate safely for 7 days of use. Aortix therapy should continue until objective signs of hemodynamic congestion have resolved, alternative / escalated therapy is required, or if device related safety concerns arise. The duration of Aortix pump use should be dictated by the physician's target for diuresis (net fluid and weight loss). In addition, the pre-specified target for pump effectiveness is a **minimum 20%** decrease in the patient's CVP and PCWP from pre-implant. **Diuretics and inotropes should not be adjusted for twelve (12) hours after the Aortix pump is turned on. After that point, while the Aortix pump is running, cessation of medications or down titration of diuretics, inotropes or other heart failure medications are allowed.** Adjustments of other medical therapy can otherwise be made at any point during the study period at the discretion of the treating physician. All medications and medications adjustments will be captured on eCRFs.

Refer to the Aortix System Instructions for Use (PPL004) for details of the Aortix Pump management.

If clinically significant device migration is suspected, use x-ray or another imaging modality to verify pump position.

It is recommended that the patient's vital signs be monitored frequently post procedurally (e.g., vitals checked every 15 minutes for the first hour, then every 30 minutes for the second hour). The patient's pedal pulses should be monitored post procedurally frequently for distal limb perfusion, ideally but not limited to, every fifteen (15) minutes times four (4), every thirty (30) minutes times two (2) and every hour (1) for two (2) hours and then as frequently as signs and symptoms warrant. In addition, the access site should be monitored for bleeding, hematoma, swelling or signs of infection.

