4.5.2.1 Programming the Pump

The Aortix Pump should initially be operated at a speed of 25 krpm for a minimum of two days. The pump may be stopped once congestion and hemodynamic targets have been achieved for that patient as assessed by the investigator. The pump should be left in place for a sufficient time to achieve the diuresis and hemodynamic goals for the patient. All adjustments are at the discretion of the investigator according to their clinical judgement. Once congestion and hemodynamic targets have been achieved, diuretic or other therapies may be down titrated or discontinued, at the physician's discretion, but the pump should be kept running at 25 krpm. **If a decision is made to reduce the Pump speed, vital signs, hemodynamic measurements and fluid ins and outs must be recorded before speed reduction in accordance with Appendix A.**

If congestion and hemodynamic targets have not been achieved after 2 days, the pump speed may be turned up in 1 krpm increments to see if running the pump at a higher speed will provide benefit to the patient.

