4.5.3 Congestion Target Met/Therapy Deemed Ineffective Data Collection

Once the congestion target has been met or therapy has been deemed ineffective, before weaning begins, the following assessments should be made within 12 hours of beginning weaning:

- Cardiovascular exam (edema, pulmonary auscultation, weight)
- Vital Signs (HR, BP, RR)
- Dyspnea evaluation
- Fluid Ins and Outs since last reading
- Hemodynamics:
 - CVP
 - PA Systolic
 - PA Diastolic
 - PA Mean
 - PCWP
 - SvO2 as measured by the PA catheter
 - SaO2 as measured by pulse oximeter
- Echocardiogram
- Blood and urine labs per Appendix A
- Document any medication changes and adverse events

If the congestion target timepoint overlaps with a scheduled assessment (e.g, an every 24 hour hemodynamic measurement), the scheduled assessment value can be used and also entered on the congestion target met timepoint eCRF.

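### The CVP/PCWP decongestion endpoint is read at a time that depends partly on the same pressures, and no fixed-time on-therapy readout is specified beside it

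*Protocol*

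**What the plan says.** **Endpoint.** Protocol 3.3.3 counts a patient as decongested if CVP or PCWP falls by at least 20%, compared "pre-implant vs when congestion target is met or therapy deemed ineffective". The BNP/NT-pro-BNP endpoint uses the same readout time. SAP 5.3 and 7.8.3 carry both forward, and the SAP 7.8.3 denominator is all As-Treated patients.

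**What sets the time.** Protocol 4.5 names a pre-specified effectiveness target of a minimum 20% "decrease in the patient's CVP and PCWP from pre-implant". It also says that the physician's own diuresis goal should govern how long the pump is used, and it puts no number on that goal. Protocol 4.5.2.1 leaves the judgement to the investigator and has the pump run at its initial speed "for a minimum of two days". BNP appears in none of these targets.

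**Which reading counts.** Protocol 4.5.3 calls for a set of assessments before weaning. If that timepoint overlaps a scheduled one, "the scheduled assessment value can be used and also entered on the congestion target met timepoint eCRF".

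**What is measured at fixed times.** Protocol 4.5.1 and Appendix A schedule CVP and PCWP at 2 h, at 24 h and then every 24 h, and BNP/NT-pro-BNP every 12 h.

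**What is reported.** SAP 7.8.3 applies the signed-rank test to pre-implant against target met. SAP 7.9.5 summarises pressures at baseline and target met, plots each patient's readings from implant, and adds a Retrieval boxplot point defined as the last on-therapy value. SAP 7.9.2 summarises laboratory values at no fixed time during therapy.

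**The concern.** The variable, the 20% cut and the readout time overlap. If the decision to stop is taken because the pressures look low, and that same reading is entered as the endpoint value, chance low readings are preferentially captured. There is no control arm in which the same selection would occur and cancel.

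The study is meant to inform the design of later studies (Protocol 7, SAP 2.3). A responder rate taken at a variable, partly outcome-dependent time does not transfer directly to a design with a fixed readout. As the SAP stands, no table would show how far the two differ.

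**Working it through.** **No plan figure to reproduce.** The documents give no variance, effect size, success threshold or power for this endpoint, and the sample size was not statistically derived (Protocol 7, SAP 2.3). The size of the effect can only be shown as a range under stated assumptions.

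**Inputs from the documents**
- Responder: fall of at least 20% in CVP or PCWP (Protocol 3.3.3, SAP 7.8.3).
- Quantified target: fall of at least 20% in CVP and PCWP (Protocol 4.5).
- Looks: daily on days 2 to 7, from the two-day minimum (Protocol 4.5.2.1) and the seven days of use for which the pump was tested (Protocol 4.5).
- The triggering value is reused (Protocol 4.5.3).

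**Assumptions, not in the documents**
- No true change.
- Log-normal within-patient variation with CV 10–20%.
- CVP–PCWP correlation 0.5.
- Readings independent from day to day.
- Stop at the first look that meets the target, otherwise read on day 7.

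**Step 1: fixed 48 h reading.** σ = √ln(1+CV²). For one pressure, p = Φ(ln 0.8 / (σ√2)). For either pressure, the rate is 2p − p₁₂, where p₁₂ is the bivariate normal probability at correlation 0.5.

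| CV | σ | z | p | p₁₂ | 2p − p₁₂ |
|---|---|---|---|---|---|
| 10% | 0.0998 | −1.582 | 0.057 | 0.015 | 0.10 |
| 15% | 0.1492 | −1.058 | 0.145 | 0.055 | 0.24 |
| 20% | 0.1980 | −0.797 | 0.213 | 0.095 | 0.33 |

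So even a fixed-time reading shows 10–33% responders from noise alone.

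**Step 2: triggered reading (simulation).** The responder definition (either pressure) is the same throughout. Only the stopping rule changes.

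| CV | Fixed 48 h | Stop when both fall | Excess | Stop when either falls | Excess |
|---|---|---|---|---|---|
| 10% | 10% | 14% | 4 | 33% | 23 |
| 15% | 24% | 33% | 9 | 59% | 35 |
| 20% | 33% | 45% | 12 | 72% | 39 |

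Small differences in set-up move the triggered figures at CV 10% by about a point (13% and 32%). In a group of 30 at CV 15%, the rates correspond to about 7 (0.24 × 30), 10 (0.33 × 30) and 18 (0.59 × 30) apparent responders.

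**Step 3: sensitivity at CV 15%**
- Looks on days 2–4 only: 24% fixed, 28% (both), 45% (either).
- Day-to-day autocorrelation 0.5: 18% at 48 h and 23% at a fixed day 7, against 30% (both) and 52% (either).
- Fresh independent reading after the trigger: 24% against 24%, no excess. If readings are autocorrelated, a fresh reading removes only part of it.
- True decline of 3% per day, autocorrelation 0.5: 29% at 48 h, 64% at a fixed day 7, 70% triggered on both. Most of the gap to 48 h is then longer treatment, not selection.

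**Step 4: BNP.** With assumed CV 25%, correlation 0.3 with each pressure and independent readings, responders are 26% at a fixed time and 27–31% at the triggered time, an excess of about 1–5 points.

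**The case against.** Several parts of the case on the other side stand.

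- **Stopping is not driven by the pressures alone.** The diuresis goal in Protocol 4.5 may dominate, and the protocol never states that the congestion target is exactly the 20% fall. The more it dominates, the smaller the selection.
- **It is not simply the best-looking reading.** Patients whose therapy is deemed ineffective are read too, and every As-Treated patient is in the denominator. Reuse of a scheduled value is allowed only where timepoints overlap. A reader might infer that the rate is inflated in all circumstances; the documents do not support that.
- **BNP does not trigger its own readout.** Because it shares the timepoint, a reader might infer the same defect. The target contains no BNP term.
- **Cumulative chances overstate the problem.** One might compute the probability of at least one either-pressure fall over all daily readings. That ignores the two-day minimum and replaces the stated both-pressures target with a looser one. The larger figures in Step 2 apply only if sites actually stop on either pressure.
- **The data are not hidden.** Protocol 7 has each patient reviewed individually, SAP 7.9.5 lists and plots the readings, SAP 7.9.2 summarises laboratory values at 72 h/discharge and follow-up, and SAP 3.1 promises nominal-time presentation where applicable. None of these is a fixed-time on-therapy responder rate or summary.
- **A fixed time is no cure for noise.** Step 1 shows this. Regression to the mean from enrolling on high CVP or PCWP (Protocol 3.4.1) is also untouched.
- **The study is small, descriptive and has no success threshold.** This argues for a supportive table, not for a change of endpoint.

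**Conclusion.** The point holds for CVP/PCWP, conditionally. When stopping follows the 20% target and the triggering reading is reused, the responder rate is biased upward relative to a fixed-time readout. Under the stated both-pressures target the excess is about 4–12 percentage points for CV 10–20%. It is about 23–39 points if sites stop on either pressure, and zero if a fresh independent reading is taken. All of these rest on assumed variances, an assumed correlation, independent daily readings and no true effect; the documents supply none of these. For BNP any bias is indirect, about 1–5 points. The firm, assumption-free part is that the SAP specifies no fixed-time responder rate or summary during therapy although the readings are already scheduled. This should be corrected, and a supportive analysis is enough.

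**What to change.** Keep the event-driven readout. Add to SAP 7.8.3 and 7.9.5, as a supportive analysis in all As-Treated patients:

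1. The percentage with at least a 20% fall in CVP or PCWP, the median change and the signed-rank test at the scheduled 24 h reading, and again at the reading nearest 48 h within a stated window. The window is needed because Appendix A lets daily readings after the first move to rounds, as little as 12 h later.
2. A rule for pumps weaned or removed before the timepoint: use the last reading before any weaning speed reduction, and report how many patients this affects. The plain last on-pump value will not do, because it may be the cath-lab reading taken after the speed was lowered (Protocol 4.5.4, 4.6.1).
3. Optionally, BNP/NT-pro-BNP at the same times, for comparability.
4. A sentence stating that the difference between the two readouts mixes timing selection with longer treatment, and that a fixed time removes neither measurement noise nor regression to the mean from selecting on high pressures.

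Three inconsistencies need reconciling at the same time:
- SAP 7.14 says the target-met timepoint is not collected in the latest CRF and substitutes another for urine output only, while SAP 7.8.3, 7.9.2 and 7.9.5 still use it.
- The target in Protocol 4.5 joins CVP and PCWP with *and*; the endpoint in Protocol 3.3.3 uses *or*.
- SAP 5.3 has a fall strictly greater than 20%, while Protocol 3.3.3 and SAP 7.8.3 include exactly 20%.

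The cost is a few table rows and no new data collection. The fixed-time figure may be less favourable.
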